Rehabilitation Compliance will be evaluated by the study team through the use of home exercise logs and interACTION reports. Logs will be reviewed at the follow-up visits with the research team. Outcome measures will be collected at baseline, 5 weeks (+/- 7 days) after enrollment, and upon discharge or a maximum of 10 weeks (+/- 7 days) after enrollment.

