### *Outcomes*

- Range of motion—Active and passive range of motion (ROM) will be measured with a standard goniometer while the patient lies in the supine position. Extension and flexion of each knee will be measured. Extension will be measured passively with a quad set and actively during a straight leg raise. The range of extension and flexion will be expressed as the difference between the involved and non-involved knees.
- Numeric Pain Rating Scale—Subjects will be asked to rate their level of pain currently and their level of worst & least pain in the past 24 hours on a scale from 0 (no pain) to 10 (worst pain imaginable).
- Activities of Daily Living Scale of the Knee Outcome Survey (ADLS)—The ADLS is a 14-item measure of symptoms and activity limitations for

individuals with a variety of knee impairments.

- Veterans RAND 12-Item Health Survey (VR-12)—The VR-12 is a 12-item patient-reported general measure of health-related quality of life that was adapted and developed from the RAND 36-Item Health Survey at the RAND Corporation and Medical Outcomes Study.
- Functional performance will also be tested in all patients. The following functional tests will be assessed at 5- and 10-week visits:
  - Six-minute Walk Test to assesses the subject's ability to walk community distances. The subject is asked to walk as far as possible in six minutes on a closed course with standing rest breaks as needed. The patient is free to use their preferred assistive device.
  - The Stair Climbing Test to test basic daily function in which a patient ascends and descends a standard flight of stairs as quickly and safely as possible, using their preferred gait pattern, assistive device, and hand rail.
  - The Timed Up and Go Test (TUG) in which the patient sits in a standard armed chair, rises, walks three meters, turns around, walks back to the chair and sits. Excessive time to complete the TUG can indicate mobility impairments and potential fall risks in elderly patients.
  - The Unilateral Balance Test in which the patient attempts to maintain single leg balance for up to two minutes, with the test ending when the patient loses balance enough to put the opposite foot on the ground.

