#### *Statistical Analysis*

For the baseline data, continuous variables were compared with the two-sample t-test and categorical variables were compared with Fisher's exact test or a chi-square test.

For the primary outcome (value, ratio of ADLS to cost), the Wilcoxon rank sum test was used to compare between the Control Group and interACTION Group. P-Values below \* $p=0.05$  were considered statistically significant for all outcomes. For the remainder of the cost analyses parameters (weeks of physical therapy, number of physical therapy visits, and total cost), a two-sample t-test was used to compare between groups.

For other clinical outcomes data, if the distribution was normal at each time point, then a repeated measures ANOVA was used. A repeated measures ANOVA was used to compare difference between groups for the ADLS, Passive ROM (flexion), and Active ROM (flexion). Otherwise, if some time points had normal data and others did not then a two-sample t-test was used for normally distributed data and the Wilcoxon rank sum test was used for non-normally distributed data.

For the functional performance tests that were assessed at the 5- and 10-week visits, a z-score (or standard score) was used to calculate a cumulative score for the Six-minute Walk Test (distance in feet), Stair Climb Test (time divided by steps), TUG (time), and Surgical Unilateral Balance (time). The z scores are the average of the z scores for each of the functional tasks. On average, the z scores are close to zero, meaning that the overall individuals within the group, the scores for each subject are not different than the mean score across all subjects.

Differences between the cumulative z-scores were assessed using a two-sample t-test.

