#### *Inclusion criteria*

Males and females between 40 and 80 years of age that have undergone primary unilateral TKA who have been referred for post-operative outpatient physical therapy will be eligible to participate in this study. Additionally, eligible subjects also need to be able to perform pre-defined exercises that they would normally

perform in a physical rehabilitation program.

The Physical therapists that will be asked to complete the Clinician Survey must have a patient participating in the study to be considered eligible.

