#### *Exclusion Criteria*

- Individuals outside the aforementioned age range (Adults <40 or >80 years of age)
- Patients with BMI >40 at the time of surgery (shown to predict poorer outcomes)
- Individuals who are not free of any co-disability or comorbidity that would specifically impede, disallow, or otherwise hinder performance of rehabilitation exercises
- Individuals who cannot physically receive or understand audio and visual feedback from the joint motion tracking system during or after performance of rehabilitation exercises.

This information will be acquired through the initial patient screening questionnaire given to potential participants during the recruitment period. These participants will be interviewed about their ability to use electronic data in the form of audiovisual feedback, about existing or pre-existing conditions that could negatively influence rehabilitation measures outlined in this study, and patients will be made aware that assistive devices can be used during the collection of all outcome measures.

The motion tracking sensors utilized in this study contain a wireless Bluetooth module that has been approved by the FCC and will not interfere with devices such as pacemakers, defibrillators, or other indwelling devices and therefore these patient's will not be specifically excluded.

Informed consent will be obtained after the screening procedures have been performed, but prior to performing any of the research interventions/interactions. The information obtained during screening is not of a sensitive nature and will only be used to determine if the subject is eligible for full participation in the study.

Participation in this study is completely voluntary. An investigator will go over the consent form with each participant who will then have the opportunity to ask questions and decide to participate. There is no possibility of coercion, as coercion to enroll in a research study would not depend on the research staff providing clinical care. Participation in this study does not influence current or future clinical care the participant may be undergoing.

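### The functional composite is compared without covariates, although baseline ADLS is already collected and adjusting for it would probably gain precision at almost no cost

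*Combined protocol and SAP*

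**What the plan says.** The Outcomes section lists the six-minute walk, stair climb, Timed Up and Go (TUG) and unilateral balance tests, and gives their timing: "The following functional tests will be assessed at 5- and 10-week visits". So there is no baseline functional score. The Statistical Analysis section averages the z-scores of the four tests and then states: "Differences between the cumulative z-scores were assessed using a two-sample t-test". It names no covariate, and does not say whether one test is done per visit or which visit matters most.

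For outcome measures in general, the Methods section says "Outcome measures will be collected at baseline, 5 weeks (+/- 7 days) after enrollment", with a last assessment at discharge or at 10 weeks at most. The Outcomes section confines only the functional tests to the two later visits, so ADLS, pain, range of motion and VR-12 are measured at baseline. The only stated use of baseline data as such is a between-arm comparison: "For the baseline data, continuous variables were compared with the two-sample t-test". That section does not list the variables compared.

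Age and BMI appear as eligibility items. Age is a criterion ("Males and females between 40 and 80 years of age"), and BMI has an upper limit of 40. Of the eligibility details, the Exclusion Criteria section says "This information will be acquired through the initial patient screening questionnaire given to potential participants during the recruitment period", and of the information obtained at screening that it "will only be used to determine if the subject is eligible for full participation in the study".

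**The concern.** ADLS and flexion range of motion have a baseline value and are planned for repeated-measures ANOVA. The functional composite gets only a post-treatment contrast. It is the trial's performance-based evidence on whether patients do as well with fewer clinic visits, a claim made under Potential Benefits, and such a claim needs a narrow interval.

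The missing baseline functional test may suggest that adjustment is impossible without an extra procedure. It is not. ADLS measures knee symptoms and activity limitations, so it is a plausible predictor of walking, stair climbing and rising from a chair. If it is one, the t-test leaves in the error term variance that could be removed, and the interval is wider than it need be.

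**Working it through.** **Inputs from the documents.** 60 patients, 30 per arm (Abstract and Methods); significance level 0.05 (Statistical Analysis), taken here as two-sided because sidedness is not stated.

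**Assumptions.** The documents give no effect size, SD, power or dropout rate for the composite, so there is no planned figure to reproduce. Differences are in SDs of the composite. R² is the within-arm share of composite variance that baseline ADLS explains; 0 to 0.30 is shown.

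**Step 1: planned analysis.** The standard error is √(2/n) = √(2/30) = 0.258 SD, with 58 degrees of freedom. For a 0.6 SD difference the noncentrality is 0.6/0.258 = 2.32, and power from the noncentral t is 62.8%.

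**Step 2: adjusting for k covariates.** The residual variance is multiplied by (1 − R²). Chance imbalance in the covariates costs an expected factor of 1 + k/(2n − k − 3), and degrees of freedom fall to 2n − 2 − k. For ADLS alone (k = 1, n = 30) the cost factor is 1 + 1/56 = 1.0179, with 57 degrees of freedom.

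| R² | Variance ratio (1 − R²) × 1.0179 | SE ratio | Equivalent total N = 60/ratio | Power at 0.6 SD |
|---|---|---|---|---|
| 0 | 1.018 | 1.009 | 58.9 | 62.0% |
| 0.10 | 0.916 | 0.957 | 65.5 | 66.5% |
| 0.20 | 0.814 | 0.902 | 73.7 | 71.6% |
| 0.30 | 0.713 | 0.844 | 84.2 | 77.2% |

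**Step 3: break-even.** Adjustment stops helping when (1 − R²) × 1.0179 = 1, that is at R² = 1 − 1/1.0179 = 0.018. If dropout left 25 or 20 analysed per arm, the cost factors would be 1 + 1/46 and 1 + 1/36, and break-even 0.021 and 0.027.

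**Step 4: three covariates (ADLS, age, BMI).** The cost factor is 1 + 3/54 = 1.056, with 55 degrees of freedom. At a joint R² of 0.10 to 0.30 the SE falls by 2.5% to 14%, the equivalent N is 63 to 81, and power at 0.6 SD is 65% to 76%. If the three explain nothing, the SE rises by 2.7%. Break-even is about 0.05, or 0.08 with 20 per arm. Age and BMI therefore help only if they add enough explained variance beyond ADLS to pay this larger cost.

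These figures are for one visit. Any further gain from modelling both visits together is not counted.

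**The case against.** The strongest reply is that nothing here is wrong. Under randomization the unadjusted t-test is valid, and its standard error already allows for chance imbalance. A reader might infer that the comparison is biased because baseline status is ignored; the documents do not support that. The composite is also a secondary outcome in a self-described pilot, and the primary outcome is the ratio of ADLS to cost. All of this stands, and limits the point to efficiency.

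Second, predictive value is not shown. Patients enrol after surgery, before their first outpatient therapy visit, so baseline ADLS may largely reflect acute post-operative limitation, and R² could be near the low end. This also stands. It matters less than it seems, because the cost of being wrong is about 0.9% of the standard error.

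Third, a reader might infer that age and BMI are equally available as covariates. The documents do not establish this. Both appear only as eligibility items, and screening information is limited to the eligibility decision. The baseline comparison may include them, but it lists no variables. The remark that BMI predicts poorer outcomes concerns values above 40, and those patients are excluded.

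Fourth, the simple formula 60/(1 − R²) would suggest 67 to 86 patients for R² of 0.10 to 0.30. It ignores the cost of estimating the covariates and is somewhat too favourable.

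Fifth, the section averages walk distance and balance time (higher is better) with stair time and TUG time (higher is worse), and states no sign reversal. Without reversal the components partly cancel, and the assumed R² loses its basis. This stands as a condition.

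Finally, the section is in the past tense and describes how the z-scores turned out. If the comparison has already been made, an adjusted model is post hoc and must be labelled so.

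**Conclusion.** The point holds as a free improvement, not as an error or a source of bias. The plan leaves unused a baseline measure that it already collects. Adjusting for baseline ADLS alone would cut the standard error of the functional comparison by about 4% to 16% if it explains 10% to 30% of composite variance, and would cost about 0.9% if it explains nothing. R² is an assumption throughout, so the direction of the gain is likely and its size unknown. The figures also assume 30 analysed per arm, two-sided testing and sign-aligned components.

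A reader might also take the composite to be the trial's only objective evidence on recovery. It is not: range of motion is measured by goniometer. The composite is the only performance-based outcome.

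**What to change.** - Replace the t-tests on the composite by ANCOVA at each visit, or by one linear mixed model for the 5-week and final visits with arm, visit and arm-by-visit, adjusted for baseline ADLS.
- Report the adjusted difference at the final visit with its 95% confidence interval. Refer to the final visit, not a fixed 10 weeks, because that assessment may take place at discharge.
- Keep the two-sample t-test as a sensitivity analysis.
- Add age and BMI only if the protocol lists them as recorded study data, which means amending the restriction on screening information.
- State that stair-climb and TUG times are sign-reversed before averaging, so that a higher composite always means better function.
- If the unadjusted comparison has already been made, report the adjusted analysis as post hoc.

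The cost is a few sentences in the Statistical Analysis section and slightly more analysis. ADLS adjustment needs no new visit, test or patient burden.

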#### *Recruitment Methods*

Recruitment will be primarily done through UPP/CMI Orthopaedic Surgery clinics, which routinely care for patients that have undergone TKA. Patients will be identified through physicians who will be the primary medical provider in their perioperative care. Prior to the patient's first outpatient physical therapy visit, the study's research coordinator or research assistant will screen these patients, using the provided screening form, for inclusion/exclusion criteria and enroll/randomize those who meet the study's parameters. Subjects will not be recruited from skilled nursing facilities.

Recruitment flyers for the study will be made available at Orthopaedic Clinics and also at the Physical Therapist Outpatient Clinics. The flyer will be used to give potential patients information about the study and to enable them to contact us if they would like to participate. Potential patients may also be given flyers if they desire, so that they may have the contact information for the study in the event that the potential patient has any questions or concerns regarding the study.

#### *Inclusion criteria*

Males and females between 40 and 80 years of age that have undergone primary unilateral TKA who have been referred for post-operative outpatient physical therapy will be eligible to participate in this study. Additionally, eligible subjects also need to be able to perform pre-defined exercises that they would normally

perform in a physical rehabilitation program.

The Physical therapists that will be asked to complete the Clinician Survey must have a patient participating in the study to be considered eligible.

#### *Exclusion Criteria*

- Individuals outside the aforementioned age range (Adults <40 or >80 years of age)
- Patients with BMI >40 at the time of surgery (shown to predict poorer outcomes)
- Individuals who are not free of any co-disability or comorbidity that would specifically impede, disallow, or otherwise hinder performance of rehabilitation exercises
- Individuals who cannot physically receive or understand audio and visual feedback from the joint motion tracking system during or after performance of rehabilitation exercises.

This information will be acquired through the initial patient screening questionnaire given to potential participants during the recruitment period. These participants will be interviewed about their ability to use electronic data in the form of audiovisual feedback, about existing or pre-existing conditions that could negatively influence rehabilitation measures outlined in this study, and patients will be made aware that assistive devices can be used during the collection of all outcome measures.

The motion tracking sensors utilized in this study contain a wireless Bluetooth module that has been approved by the FCC and will not interfere with devices such as pacemakers, defibrillators, or other indwelling devices and therefore these patient's will not be specifically excluded.

Informed consent will be obtained after the screening procedures have been performed, but prior to performing any of the research interventions/interactions. The information obtained during screening is not of a sensitive nature and will only be used to determine if the subject is eligible for full participation in the study.

Participation in this study is completely voluntary. An investigator will go over the consent form with each participant who will then have the opportunity to ask questions and decide to participate. There is no possibility of coercion, as coercion to enroll in a research study would not depend on the research staff providing clinical care. Participation in this study does not influence current or future clinical care the participant may be undergoing.

#### *Risks*

Patients will perform a standard rehabilitation while wearing IMU motion-tracking sensors. A software application running on a tablet will wirelessly collect sensor data, display live motion data to guide patient performance of exercise tasks, and send performance data to servers for online review by the subject's physical

therapist. As these are standard rehabilitation exercises, there is no increased risk of pain or injury in performing these activities compared to the current standard method of performing the exercises. There is no risk of impaired rehabilitation due to decreased supervision. The use of IMU motion-tracking sensors poses no likely increased risk of physical or mental pain, or distress to the study subjects. There is no risk to the patients or others in their household of interference with in-dwelling electronic devices such as pacemakers or defibrillators.

Exercise data will be stored on both the tablet device and also transmitted during participant session. This data is de-identified, and the device is password protected using the device's native security. The data will be encrypted via SSL during transmission to the Microsoft Azure Cloud server, and also when accessing that server from Pitt's internal servers.

Data sharing was not identified or planned in this version, including contacts, texts, and geo-location information. As mentioned before, to prevent interception of exercise data, Exercise data will be stored on both the tablet device and transmitted during participant session. This data is de-identified, and the device is password protected using the device's native security. The data will be encrypted via SSL during transmission to the Microsoft Azure Cloud server, and when accessing that server from Pitt's internal servers.

The most likely infrequent risk to the subject may be discomfort from wearing the sensors as well as potential spillage of water/fluids on the device which could interfere with its functioning; however, there is no risk of electrical shock if the device gets wet. This device is designed to be comfortable to wear and is based on commonly used, commercially available body straps, and will come with usage precautions. Some subjects may also experience mild skin irritation from sweat build-up where the straps are worn. Patients will be able to communicate with their therapists in weekly visits or by phone regarding painful events or difficulties with exercise.

Participants will perform several different strength tests. Risks of injury will be minimized by allowing adequate time for warm-up, stretching, and familiarization with the task. Qualified individuals will administer the tests. Participants will be closely monitored by a member of the study staff. In the event that the participant needs first aid treatment, a certified athletic trainer, physical therapist, or orthopaedic surgeon will administer the appropriate care.

Participant confidentiality will be maintained at all times. All records will be assigned a case number. Information collected in this study will be stored in a locked file cabinet in a secure office and will be accessible only to the research staff. Electronic files will be stored on the UPMC and/or Pitt secure networks behind the firewall. Subjects will not be identified in any publications or presentation of the research results.

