### *Methods*

Sixty patients following total knee arthroplasty will be monitored for up to 10 weeks during their outpatient physical therapy course. For the control group, 30 of these patients will undergo two to three weekly sessions with a physical therapist supplemented by unmonitored home-based exercises. The second group of 30 patients will fulfill their rehabilitation course with one to three sessions per week with a physical therapist and will use the interACTION home rehabilitation monitoring program to supplement these sessions. The patients in the interACTION group will use the device for the first two weeks of their rehabilitation in the clinic in order to become familiar with the device before home use. After the first two weeks the patient will be asked to take the device home and reduce their weekly outpatient visits by one visit per week. However, if the physical therapist feels it is best for the patient to deviate from the protocol, this is allowed. At the end of the 10-week rehabilitation course, rehabilitation compliance, costs, and patient outcomes will be analyzed for differences between the two groups.

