A web-accessible, password-protected portal allows a local or remote physical therapist to monitor the patient's progress. Physical therapists have access to the data to analyze patient progress and compliance and review computer-generated alerts. Capabilities in the clinician portal include assessment of patient data during exercises and activities of daily living (ADLs), weekly progress reports by reviewing changes in important variables (i.e. range of motion, pain, patient-reported activity, participation, quality of life). The ability to monitor progress ensures the patient's compliance to the treatment program and allows clinicians to update the patient's exercise regimen as needed.

Use of the interACTION system has the potential to allow physical therapists to improve patient-oriented outcomes, streamline utilization of clinical resources, and provide care more efficiently for a larger number of patients. In turn, patients will be more confident and compliant with performance of their prescribed exercise program and will receive feedback on their recovery progress. However, research is needed to demonstrate these hypothesized benefits of the interACTION system.

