## **Methods**

For this randomized treatment study, we will recruit 60 patients that have undergone total knee arthroplasty (TKA) that are being referred for post-operative outpatient physical therapy. After obtaining informed consent, and upon successful

screening/recruitment, subjects will be randomly assigned to one of two groups:

1. Control Group: Rehabilitation performed by a physical therapist and supplemented with a home exercise program for a maximum of ten weeks. Therapy will consist of two to three visits per week as prescribed by the physical therapist and based on the best interest of the patient. Patients will record their performance of the prescribed home exercise programs on a paper-based exercise log on a daily basis.
2. InterACTION Intervention Group: Rehabilitation performed by a physical therapist and supplemented by use of interACTION for a maximum of ten weeks. This will include two to three visits per week for two weeks in which the patient will use interACTION during routine outpatient physical therapy sessions to familiarize them with the system. After two weeks, the patient will be issued an interACTION device for home use that will guide them through their exercise program. At this point subjects in the interACTION group should continue to return to the outpatient rehabilitation facility, but reduce their weekly routine visit with their physical therapist by one during the next eight weeks of recovery, while concurrently using interACTION at home. Patients who attended two visits per week for the first two weeks should subsequently attend one visit per week. Patients who attended three visits per week for the first two weeks will subsequently attend one to two visits per week. However, if the physical therapist feels it to be in the best interest of the patient to deviate from the protocol, this is allowed.

*Note: InterACTION is currently under development, not a commercial application. The 3rd Party Developer was OpenArc, LLC ([name]). The mobile application is currently supported on a Nexus tablet with Android operating system (specifically lollipop and kitkat versions). The mobile application and the kinematic sensors will be provided to the participant, the participants will NOT use a personal device.*

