#### *Potential Benefits*

This study aims to increase knowledge related to use of the interACTION device to supplement post-operative rehabilitation after TKA. If the interACTION device leads to improved post-operative outcomes, patients in the future would benefit from use of the device to supplement their post-operative rehabilitation program. If beneficial, use of the interACTION device would result lead to the same or better outcomes with fewer in-clinic physical therapy visits, thus improving the value of care with lowered healthcare costs and expenditures.

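### The Risks section rules out impaired rehabilitation from reduced supervision, which the trial has yet to show, and the supplied text plans no count of readmission or re-operation by arm

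*Combined protocol and SAP*

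**What the plan says.** The Risks section says "There is no risk of impaired rehabilitation due to decreased supervision". It attaches no data and no qualification.

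Under Methods, both arms attend two to three times a week at first. After two weeks, interACTION patients alone are to "reduce their weekly routine visit with their physical therapist by one during the next eight weeks of recovery". Patients who started at two visits go to one, and those who started at three go to one or two. The therapist may override this: "if the physical therapist feels it to be in the best interest of the patient to deviate from the protocol, this is allowed".

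Two features work in the interACTION arm's favour. The tablet will "send performance data to servers for online review" by the therapist, and Background adds that "Physical therapists have access to the data to analyze patient progress and compliance and review computer-generated alerts". Control patients, according to the Abstract, have clinic sessions "supplemented by unmonitored home-based exercises".

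Elsewhere the effect is treated as unknown. Background says that "research is needed to demonstrate these hypothesized benefits of the interACTION system". Potential Benefits makes "same or better outcomes with fewer in-clinic physical therapy visits" conditional on the device proving beneficial. The Purpose paragraph describes a pilot meant to find out whether the approach improves compliance and rehabilitation.

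The Abstract and Background both list readmission and further surgery among the consequences of poor compliance.

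**The concern.** A flat statement of no risk settles in advance a question that the trial exists to answer, and it does so for the arm whose in-person contact is cut. Risk text should describe what is uncertain.

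The second part is a recording gap. The plan names readmission and re-operation as consequences of the behaviour that the trial tries to change, yet none of its data collection provides for counting them. If a patient in either arm were readmitted or re-operated on, following the plan as written would give no tally by arm. The event might show only indirectly, as a worse score or a missing visit. A report that the reduced-visit schedule was safe would then have no event count behind it.

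**Working it through.** There is no figure in the plan to reproduce: it gives no event rate, margin or power calculation. The check is a comparison of texts with some supporting arithmetic.

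**1. Is in-person contact reduced, and in which arm?** Inputs are the weekly frequencies and the ten-week maximum in Methods. I assume a constant frequency, the full ten weeks and no therapist deviation. Visits in weeks 3 to 10 = weekly visits × 8. The ten-week total adds the first two weeks.

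| Starting frequency | Control, weeks 3–10 | interACTION, weeks 3–10 | Control, 10 weeks | interACTION, 10 weeks |
|---|---|---|---|---|
| 2, then 1 | 2×8 = 16 | 1×8 = 8 (50% fewer) | 20 | 2×2+8 = 12 |
| 3, then 2 | 3×8 = 24 | 2×8 = 16 (33% fewer) | 30 | 3×2+16 = 22 |
| 3, then 1 | 3×8 = 24 | 1×8 = 8 (67% fewer) | 30 | 3×2+8 = 14 |

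The last row goes beyond the general instruction to drop one visit, but Methods allows it for three-visit patients. Earlier discharge or therapist override would change these counts. They measure clinic contact, not harm.

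**2. Does the plan treat the consequence as known?** No. Purpose, Background and Potential Benefits each leave it open, as quoted above. Only the Risks sentence treats it as settled.

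**3. Would impaired rehabilitation be seen?** Yes, to a useful extent. Outcomes lists range of motion, pain, ADLS, VR-12 and functional tests. Statistical Analysis provides for comparing clinical and functional results between groups, and compares the number of physical therapy visits.

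**4. Would a readmission or re-operation be counted?** The possible places are:
- Outcomes and compliance logs: neither event is listed.
- Cost parameters in Statistical Analysis: therapy weeks, therapy visits and total cost. Total cost is not defined, so a reader cannot tell whether hospital care enters it. Even if it does, it is not a count of events.
- Exit interview: open-ended, covering experiences and expenses, so an event would surface only by chance.
- Reporting painful events to the therapist, and first aid during testing (both in Risks): no recording rule is given.
- Clinician Survey, screening form and consent pages: not available for review, so nothing can be concluded from them.

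**5. What could counts show with 30 per arm?** The exact two-sided 95% upper limit for 0 of 30 is 1 − 0.025^(1/30) = 0.116, or 11.6%. For 1 of 30 the exact limits are about 0.08% and 17.2%. Counts of this size can describe but cannot support a comparison.

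**The case against.** The best defence is that supervision is redistributed and may not be lost. Background describes traditional rehabilitation as one to three outpatient sessions a week, so the reduced schedule of one to two lies inside ordinary practice. The interACTION arm also gains remote review with alerts, control home exercise is unmonitored, and the therapist can restore visits at any time. All of this stands. Net supervision could be lower or higher, and the percentages in the table should not be read as a loss of care. These are reasons to call the risk reduced. They do not justify calling it absent.

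A second objection is that the two halves are loosely joined. The plan ties readmission and further surgery to poor compliance, not to fewer visits, and the monitored arm is expected to comply better. That is also correct. The case for recording these events rests on compliance being the trial's target, and it applies equally to both arms.

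A reader might infer three stronger things:
- *The reduced schedule harms patients.* Nothing in the documents shows that.
- *The trial cannot detect poor recovery.* It can, through the planned clinical and functional outcomes.
- *The primary result is compromised.* The value ratio is compared with a rank test, so one very costly patient has a limited influence, and total cost may already include such care. The documents support no claim about the primary test.

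**Conclusion.** The point holds in a narrow form. The no-risk sentence is unsupported by the plan's own text and should be changed. Separately, the supplied text contains no plan to record readmission or re-operation by arm. This is a cheap improvement of minor weight, something to consider rather than a flaw in the comparison.

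The visit differences (8 to 16 fewer nominal visits over ten weeks) rest on full-length therapy at a constant frequency without therapist override. The statement that no count is planned covers only the supplied text, and event reporting could sit in the survey or consent material. It would therefore be wrong to conclude that the investigators had no safety reporting at all. Confidence is medium for that reason.

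**What to change.** 1. Replace the sentence in Risks with: *Slower or poorer recovery with fewer supervised clinic visits is possible and is being studied.*
2. At the existing 5-week and discharge or 10-week visits, ask both arms the same short question about readmission, re-operation and unscheduled care other than physical therapy, since enrollment or since the last visit.
3. Report counts by arm descriptively, giving the time window covered, because discharge can come before week 10. Do not run a significance test.
4. In Statistical Analysis, state whether total cost includes such care. No separate costing analysis is needed.

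The cost is one sentence of risk text, one clarifying sentence on cost, and a short form at visits already scheduled. Statistical Analysis is written in the past tense. If follow-up is already complete, the sentence can still be corrected and the absence of event counts reported as a limitation.
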